12.3 Post-ablation Follow-up Visits

The list of assessments is the same for all follow-up visits unless otherwise specified.

At each follow-up visit, the patient will visit the site (or have a tele-visit and/or phone visit when unable to visit the site) and the following assessments will occur:

- Evaluate ECOG performance status (Visit 3 only). After Visit 3, evaluate ECOG, if applicable per site SOC. ECOG may be assessed over the phone.
- Laboratory tests, as follows, if applicable per site SOC:
 - Coagulation tests, including, INR, PT and APTT (or PTT).
 - Liver function tests, including AST, ALT, GGT, albumin, direct and total bilirubin, and total protein.
 - Renal function tests, including BUN, creatinine and electrolytes (sodium, potassium, chloride and bicarbonate).
 - CBC, including differential cell count and platelet count.
 - Genetic markers including: Alpha-fetoprotein (AFP) level, Carbohydrate antigen 19-9 (CA19-9) level, Carcinoembryonic antigen (CEA).
- Record all relevant concomitant medications: Relevant concomitant medications include: chemotherapy, immunotherapy, blood-thinning or coagulation, NSAIDs, those medications used to treat AEs, those used for hepatitis (if concurrently treating), and any others that are relevant in the opinion of the investigator. Relevant concomitant medications may be assessed over the phone.
- QOL questionnaires, using EORTC QLQ-C30 and liver-specific QLQ-HCC18, (Visits 3 through 6). The questionnaires may be administered over the phone, as needed.
- Pain score using the Numeric Pain Rating Scale (Visit 3 only). The questionnaire may be administered over the phone, as needed.
- Technique efficacy evaluation (Visit 3 only).
- Imaging to determine whether there has been a local or regional recurrence of lesion(s). If there is a recurrence, determine soft tissue liver lesion details via CT, MRI, PET, US, and/or X-ray.
 - All SOC scans of the abdomen/liver (CT, MRI, and/or PET) should be submitted to the Sponsor.
- Record relevant concomitant procedures (i.e. liver or lesion-related). Relevant concomitant procedures may be assessed over the phone.

- Record follow-up post-ablation treatment, including the number of successful repeat ablations, if applicable, and if patient has been hospitalized since the procedure. If patient has been re-ablated with NeuWave, record ablation procedure details as outlined in section 19.1, subsection 1.

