14.0 DEVIATIONS FROM THE CLINICAL REGISTRY PLAN

A protocol deviation is any noncompliance with the registry protocol, Good Clinical Practice, or protocol-specific requirements. A deviation (any activity conducted outside the parameters established by the registry protocol) can be identified from a number of sources. Potential sources include but are not limited to: a member of the Investigator's staff, a Sponsor representative during monitoring visits, or a member of the data management or statistical groups when entering or analyzing data. Regardless of the source, it is crucial to document the deviation in the protocol deviation eCRF. The Investigator will report protocol deviations to the IRB/EC as required by the IRB/EC procedures.

Any deviation from the protocol or procedures should be recorded in the source documents. Assessments or visits that are not completed because they are not SOC at a site, or assessments that were not completed for retrospective patients, should not be considered protocol deviations.

Steps to be taken to assure the accuracy and reliability of data include the selection of qualified investigators and appropriate sites, the review of protocol procedures with the Investigator and associated personnel prior to the registry, and periodic monitoring visits by the Sponsor. The Sponsor will review eCRFs for accuracy and completeness during monitoring visits; any discrepancies will be resolved with the Investigator or designees, as appropriate.

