1.2 Study Design

This is a multicenter, observational registry that follows patients for a total of up to 5 years from the date of the first liver ablation procedure with either the NEUWAVE Microwave Ablation System or the NEUWAVE Microwave Ablation System with Ablation Confirmation.

This is an “umbrella registry,” which was included as an optional component in other NEUWAVE studies; hence, data from consenting patients who are or will be enrolled in other NEUWAVE soft tissue liver lesion ablation studies will be included in this registry. All other patients will be enrolled and followed prospectively, enrolled retrospectively with prospective, longitudinal follow up, or enrolled retrospectively with all retrospective follow up.

2 Treatment Assignment

This is a single-arm registry where all enrolled patients will be ablated using the NEUWAVE Microwave Ablation System as part of the site’s SOC treatment or per protocol for those patients who are also enrolled in other NEUWAVE studies.

3 Randomization and Blinding Procedures

As this is a single-arm registry, no randomization will occur, and no blinding procedures are required.

4 Interval Windows

Interval windows are provided in the Schedule of Assessments section of the study protocol. No additional windows are planned for analysis purposes.

5 Levels of Significance

No levels of significance are specified as no specific hypotheses about any of the outcomes of interest are being formulated or tested. Two-sided 95% confidence intervals (CI) will be estimated for specific endpoints for descriptive purposes only.

6 Analysis Sets

All Enrolled Set (AES): Consists of subjects who signed informed consent form or retrospectively enrolled with a waiver for signing informed consent form. The AES will be used for disposition of study subjects.

Full Analysis Set (FAS): FAS Consists of subjects who met inclusion/exclusion criteria and to whom the NeuWave Ablation device was utilized during procedure. Primary and secondary endpoints will be analyzed using FAS.

Safety Analysis Set (SAF): SAF Consists of subjects who met inclusion/exclusion criteria and to whom the NeuWave Ablation device was utilized during procedure. Safety endpoints will be analyzed using SAF.

7 Sample Size Justification

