8.4.1 Primary Endpoint

Perioperative endpoint-

1. Technical success, defined as ablation of the target lesion(s) according to the protocol and covered completely, with an adequate margin, as defined by the performing physician (i.e., the ablation zone completely overlaps or

encompasses the target lesion(s) plus an ablative margin), as assessed by CT, MRI, PET, US, and/or X-ray, immediately following the procedure. Technical Success is assessed at Visit 2 following the ablation of the target lesion.

Short term endpoint -

2. Technique efficacy, ablation of the target lesion(s) according to the protocol and covered completely, with an adequate margin, as defined by the performing physician (i.e., the ablation zone completely overlaps or encompasses the target lesion(s) plus an ablative margin), as assessed by CT, MRI, PET, US, and/or X-ray, at Visit 3 (between 7 days and less than 3 months post-ablation).

Long term endpoint -

3. Target lesion recurrence (local recurrence) rate evaluated at every visit starting from visit 4 after the primary ablation at visit 2 of the target lesion(s), and overall evaluation at the 5-year follow-up, as assessed by CT, MRI, PET, US, and/or X-ray.

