8.5 Analysis of Primary Endpoint

The number and percentage of patients and lesions achieving technical success will be summarized and a two-sided 95% confidence interval will be provided based on Clopper-Pearson's method. Technical success is achieved when the ablation is defined as a complete ablation by the performing physician. Technical success will be summarized at patient level and at lesion level. Technical success is achieved for a patient when all ablated lesions are defined as a complete ablation by the performing physician.

The number and percentage of patients and lesions achieving technique efficacy will be summarized and a two-sided 95% confidence interval will be provided based on Clopper-Pearson's method. Technique efficacy is achieved when the ablation is defined as a complete ablation by the performing physician. Technique efficacy will be summarized at patient level and at lesion level. Technique efficacy is achieved for a patient when all ablated lesions are defined as a complete ablation by the performing physician.

Target lesion recurrence will be summarized at patient level and at lesion level. Time-to-event analysis (survival analysis) using Kaplan-Meier's method will be utilized to estimate the target lesion recurrence rate at 3-month, 6-month, up to 60-month follow up. Cumulative incidence rate will be estimated for target lesion recurrence considering death as a competing risk and estimates will be presented at 3-month, 6-month, up to 60-month follow up. A two-sided 95% CI will be estimated for target lesion recurrence. Subjects who failed technique efficacy will be excluded from the analysis for target lesion recurrence.

First occurrence of a target lesion recurrence at patient level will be considered as the “event” for time-to-event analysis.

First occurrence of a target lesion recurrence at lesion level will be considered as the “event” for time-to-event analysis.

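### The target lesion recurrence analysis excludes by subject even at lesion level, and leaves subjects with no Visit 3 technique-efficacy result unclassified

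*SAP*

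**What the plan says.** SAP 8.5 summarises target lesion recurrence at patient level and at lesion level, by Kaplan-Meier and by cumulative incidence with death as a competing risk. One sentence limits who enters: "Subjects who failed technique efficacy will be excluded from the analysis for target lesion recurrence". The same section makes patient-level technique efficacy depend on all of the patient's ablated lesions being complete.

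Technique efficacy has a single assessment point. Protocol 12.3 lists "Technique efficacy evaluation (Visit 3 only" among the follow-up assessments, and SAP 8.4.1 sets the window at 7 days to under 3 months. SAP section 4 says "No additional windows are planned for analysis purposes". Recurrence counting starts where that window ends: "Target lesion recurrence (local recurrence) rate evaluated at every visit starting from visit 4" (SAP 8.4.1). The event is simple: "First occurrence of a target lesion recurrence at patient level will be considered as the “event” for time-to-event analysis" (SAP 8.5).

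The default population is broad. SAP section 6 says "Primary and secondary endpoints will be analyzed using FAS", and that set requires only eligibility and use of the device. Imaging follows site standard of care (Schedule of Assessments, note 13). Protocol 14.0 does not treat as deviations "Assessments or visits that are not completed because they are not SOC at a site", nor assessments not completed for retrospective patients. SAP 8.11 rules out imputation and SAP 8.7 rules out sensitivity analyses.

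**The concern.** The exclusion appears intended to restrict recurrence to tumour that was completely ablated. Its wording misses that aim in two ways.

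First, the unit is wrong for one of the two analyses. A subject-wise exclusion is natural at patient level. At lesion level it also discards lesions that were shown to be complete, and it does so only in multi-lesion patients.

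Second, the rule covers failure but not absence of a result. Such subjects are foreseeable: imaging is standard of care only, retrospective patients are admitted, data on roll-over patients start at registry consent (Schedule, Note 2), and Protocol 17.9 expects missing values in the dependent variables. Neither document gives a criterion separating residual from recurrent tumour. Incomplete ablation seen inside the Visit 3 window removes the subject; the same finding first seen at Visit 4 can become an event. A primary endpoint's numerator and denominator then depend partly on scan timing, and no planned analysis would show it.

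**Working it through.** The plan states no recurrence rate, residual-tumour rate, Visit 3 completion rate or distribution of lesions per patient, so there is no figure of its own to reproduce. Both calculations below use assumed inputs.

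**1. Lesion-level loss.** Let f be the probability that a lesion fails technique efficacy, independent between lesions, and k the number of ablated lesions in the patient. A completely ablated lesion is dropped if any of the other k − 1 fails:

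loss = 1 − (1 − f)^(k−1)

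| k | f = 5% | f = 10% |
|---|---|---|
| 1 | 0 | 0 |
| 2 | 5% | 10% |
| 3 | 1 − 0.95² = 9.75% | 1 − 0.90² = 19% |

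**2. Unassessed subjects kept in.** Let u be the share with no Visit 3 result, r the share with residual tumour (taken as equal in assessed and unassessed subjects), and p the true recurrence proportion after complete ablation. Residual tumour is assumed to be always found: at Visit 3 if assessed, later if not, and then counted as recurrence. Censoring and death are ignored. N = 1500 (Protocol Summary) sets the scale only.

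- Analysed = N[(1 − u)(1 − r) + u] = N(1 − r + ur)
- Events = N[ur + p(1 − r)]
- Bias = events/analysed − p = ur(1 − p)/(1 − r + ur)

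For p = 10%, r = 5%, u = 20%: analysed = 1500 × 0.96 = 1440; events = 1500 × (0.010 + 0.095) = 157.5; observed = 10.9%.

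| p | r | u | Analysed | Events | of which residual | Observed | Bias (points) |
|---|---|---|---|---|---|---|---|
| 15% | 3% | 10% | 1460 | 222.8 | 4.5 | 15.3% | 0.3 |
| 10% | 5% | 20% | 1440 | 157.5 | 15 | 10.9% | 0.9 |
| 10% | 5% | 40% | 1455 | 172.5 | 30 | 11.9% | 1.9 |
| 10% | 10% | 30% | 1395 | 180 | 45 | 12.9% | 2.9 |
| 5% | 10% | 40% | 1410 | 127.5 | 60 | 9.0% | 4.0 |

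The first and last rows are the extremes over u = 10-40%, r = 3-10% and p = 5-15%. The 95% half-width, 1.96 × √(p(1 − p)/analysed), is about 1.1 to 1.9 points over the same grid, so the bias can be smaller or larger than the sampling error. It is zero if u = 0 or r = 0, and otherwise upward.

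**3. Would relabelling late findings as technique failure cure it?** Take p = 12%, and suppose a share g of true recurrences in unassessed subjects is already visible on a late first scan and is relabelled. Reported recurrence is 0.12(1 − ug)/(1 − 0.12ug):

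- u = 10%, g = 25%: 0.117/0.997 = 11.7%
- u = 30%, g = 50%: 0.102/0.982 = 10.4%

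The bias reverses, because entry now depends on a clear later scan.

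**The case against.** The strongest reply is that the SAP never says unassessed subjects are kept. A programmer could read failure as anything short of documented success and drop them. Investigator assessments govern all protocol-defined analyses (Protocol 11.3), and nothing tells an investigator to call never-ablated tumour a recurrence. A reader might infer that residual tumour will be counted as recurrence. The documents support only that it can be, under a literal reading. That part of the reply stands, but it leaves the rule undefined, and two readings would give two values of a primary endpoint.

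Missingness should not be overstated either. A reader might infer that any missed Visit 3 is exempt from deviation reporting; Protocol 14.0 exempts only gaps that are not standard of care at the site or that concern retrospective patients. Phone and tele-visits are for patients unable to attend. Completeness is also imaged on the ablation day, which may lower residual tumour among unassessed subjects. However, technical failure on that day does not trigger the exclusion, so it does not close the gap.

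It is also tempting to say that sites scanning late will show better technique efficacy. They would record fewer failures, but under equal residual rates the percentage among assessed subjects is unchanged. If missing results counted as not achieved, it would fall. Distortion of the Cox model is plausible but not quantified, and SAP 8.10 labels that model exploratory.

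On the lesion-level point, the wording may simply be loose, and the table shells, which are in a separate document, may handle it. The SAP text is still what governs, and it says subjects. That the estimates are descriptive does not remove the need for a defined numerator and denominator.

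**Conclusion.** The point holds in two parts. The lesion-level part follows from the text alone: a subject-wise exclusion removes completely ablated lesions of multi-lesion patients. Its size is 5-10% of such lesions with two lesions and about 10-19% with three, if failures are independent at an assumed 5-10%, and nil with one lesion.

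The second part is a gap in the rule. Subjects with no Visit 3 result are not classified and, read literally, remain at risk, so incomplete ablation first seen from Visit 4 can enter as recurrence. The direction is upward whenever such tumour is present and so recorded. The size cannot be fixed from the documents; about 0.3 to 4 points is an illustration over assumed ranges. The documents do not establish that this misclassification will occur in every such case, or that the technique-efficacy percentage is biased.

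**What to change.** In SAP 8.5:

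- State that the exclusion for failed technique efficacy is by lesion in the lesion-level recurrence analysis and by patient in the patient-level analysis.
- Classify technique efficacy as achieved, failed or not evaluable, the last meaning no Visit 3 assessment, and report the number not evaluable at both levels. For a patient with mixed results, state the rule; one consistent with the all-lesions definition is failed if any lesion failed, achieved if all are complete, otherwise not evaluable.
- Present target lesion recurrence twice: with the not-evaluable group included, and restricted to lesions or patients with success documented at Visit 3. Amend SAP 8.7 to allow this for the endpoint.

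Tumour on a late first scan should not be relabelled as technique failure. That would conflict with the Visit 3 definition in Protocol 6.2, has no criterion for separating residual from recurrent tumour, and biases recurrence downward, as shown above.

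The cost is SAP wording, any matching change to the table shells, and one additional analysis. The restricted version is smaller: 1500 × (1 − u)(1 − r) gives about 1282 patients at u = 10% and 855 at u = 40%, with r = 5%. It may also be selected, since patients scanned in the window may differ from those who were not, so neither version should be shown without the other.

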8.6 Analysis of Secondary Endpoints

The number and percentage of patients and lesions achieving secondary efficacy will be summarized and a two-sided 95% confidence interval will be provided based on Clopper-Pearson’s method. Analysis for secondary efficacy rate includes only repeat ablations for target and non-target lesions.

For patient level analysis – secondary efficacy is achieved for a patient when all re-ablations of target lesions and all re-ablations of non-target lesions are defined as a complete ablation by the performing physician. The denominator for subject level analysis will include subjects who had a re-ablation during visit 3 to visit 14 including unscheduled visits.

For lesion level analysis – secondary efficacy is achieved for a lesion when all repeat ablations of that lesion (target and non-target lesions) are defined as complete ablation by the performing physician. The denominator for lesion level analysis will include lesions that had a repeat ablation during visit 3 to visit 14 including unscheduled visits.

Regional recurrence rates will be estimated at patient level. Time-to-event analysis (survival analysis) using Kaplan-Meier’s method will be utilized to estimate the regional recurrence rate at 3-month, 6-month, up to 60-month follow up. Two-sided 95% CI will be estimated for regional recurrence rate. First occurrence of identification of a new lesion outside the initial treatment site(s) during visit 3 to visit 14 including unscheduled visits at patient level will be considered as the “event” for time-to-event analysis at patient level.

Recurrence-free survival rates will be estimated at patient level. Time-to-event analysis (survival analysis) using Kaplan-Meier’s method will be utilized to estimate the recurrence-free survival rate at 3-month, 6-month, and up to 60-month follow up. Two-sided 95% CI will be estimated for recurrence-free survival rate.

An “event” is defined for recurrence-free survival if any of the following conditions are met:

- a. First occurrence of a target lesion recurrence during visit 4 to visit 14 including unscheduled visits at patient level
- b. Identification of a new non-target lesion during visit 3 to visit 14 including unscheduled visits at patient level

c. Deaths from any cause of a patient during the follow up period

Overall survival rate will be estimated at 3-month, 6-month, and up to 60-month follow up using Kaplan-Meier's method. Two-sided 95% CI will be estimated for overall survival rate.

Scores from the EORTC QOL questionnaires and Numeric Pain Rating Scales will be summarized with methodology consistent to the recommendations of the specific survey. Economic impact of ablation by capturing procedure-related items will be summarized with descriptive statistics.

Incidence of adverse events (AEs) (SAEs) that are deemed at least unlikely related to the procedure or device and all serious adverse events (SAEs) from the start of the ablation procedure through the end of the study will be summarized by MedDRA system organ class (SOC) and preferred term (PT).

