9. If applicable, per site SOC: genetic markers include Alpha-fetoprotein (AFP), Carbohydrate antigen 19-9 (CA19-9), Carcinoembryonic antigen (CEA)
10. Record all relevant prior medications taken within 60 days prior to Visit 2 and all relevant concomitant medications taken throughout the registry. Relevant concomitant medications include: chemotherapy, immunotherapy, blood-thinning or coagulation, NSAIDs, those medications used to treat AEs, those used for hepatitis (if concurrently treating), and any others that are relevant in the opinion of the investigator. For post-ablation follow-up visits, relevant concomitant medications may be assessed over the phone, as needed.
11. Quality of Life questionnaires: EORTC QLQ-C30 and liver-specific QLQ-HCC18. The questionnaires may be administered over the phone, as needed.
12. Pain score, using the Numeric Pain Rating Scale. The questionnaire may be administered over the phone, as needed.
13. Use SOC imaging for all study visits.
14. Ablation procedure details, as listed in Section 19.1 of the protocol.
15. Healthcare provider parameters, as listed in Section 19.1 of the protocol.
16. SOC imaging as used at every follow-up visit to determine if there is local or regional recurrence of lesion(s). If there is a recurrence, determine soft tissue lesion details, via CT, MRI, PET, US, and/or X-ray. Scans will be submitted to the Sponsor (refer to NOTE 1).
17. Record only relevant concomitant procedures (i.e. liver or lesion-related). For post-ablation follow-up visits, relevant concomitant procedures may be assessed over the phone, as needed.
18. Technical success, defined as ablation of the target lesion(s) according to the protocol and covered completely, with an adequate margin, as defined by the physician performing the ablation (that is, the ablation zone completely overlaps or encompasses the target lesion plus an ablative margin), as assessed by CT, MRI, PET, US, and/or X-ray, immediately following the procedure. If patient has had any lesions ablated with NeuWave in the post-ablation follow-up visit period, assess Technical success following each ablation.
19. Technique efficacy, defined as ablation of the target lesion(s) according to the protocol and covered completely, with an adequate margin, as defined by the physician performing the ablation (that is, the ablation zone completely overlaps or encompasses the target lesion plus an ablative margin), as assessed by CT, MRI, PET, US, and/or X-ray, at Visit 3.

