8.4.2 Secondary Endpoints

Secondary endpoints of this registry are:

1. Secondary efficacy rate, defined as the percentage of soft tissue lesions that have undergone successful repeat ablations (target or non-target) following identification of local soft tissue lesion progression. A successful repeat ablation will be defined as ablation of the lesion according to the protocol and covered completely, with an adequate margin, as defined by the performing physician (i.e. the ablation zone completely overlaps or encompasses the lesion plus an ablative margin), as assessed by CT, MRI, PET, US, and/or X-ray, immediately following the procedure.

2. Regional recurrence rate at a separate location in the liver (outside the initial treatment site(s)), evaluated at every visit after ablation of the target lesion(s), and overall evaluation at the 5-year follow-up, as assessed by CT, MRI, PET, US, and/or X-ray.

3. Recurrence-free survival, evaluated at every visit after ablation of the target lesion(s), and overall evaluation at the 5-year follow-up, as assessed by CT, MRI, PET, US, and/or X-ray.

4. Overall survival, evaluated at every visit after ablation of the target lesion(s), and overall evaluation at the 5-year follow-up.
5. Assess economic impact of ablation by capturing procedure-related items such as: complete procedure duration, ablation duration, number of ablations, length of hospital stay, and number and types of probes used.
6. Incidence of adverse events (AEs) (SAEs) that are deemed at least unlikely related to the procedure or device and all serious adverse events (SAEs) from the start of the ablation procedure through the end of the study.
7. Two QOL questionnaires: European Organization for Research and Treatment of Cancer (EORTC) QLQ-C30 and liver-specific QLQ-HCC18.

Note: These two questionnaires were chosen as tools to assess overall health status/quality of life in the patient population with soft-tissue liver lesions.
8. Numeric Pain Rating Score.

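### SAP 8.6 credits secondary efficacy only when every repeat ablation was complete and omits the local-progression condition, so the reported rate is not the endpoint as defined

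*SAP*

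**What the plan says.** **Definition.** SAP 8.4.2, in the same words as Protocol 6.3, defines the secondary efficacy rate as "the percentage of soft tissue lesions that have undergone successful repeat ablations (target or non-target) following identification of local soft tissue lesion progression". It then says what makes one such ablation a success: "A successful repeat ablation will be defined as ablation of the lesion according to the protocol and covered completely, with an adequate margin", as judged by the performing physician on imaging straight after the procedure.

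**Scoring.** SAP 8.6 sets the lesion-level rule: "secondary efficacy is achieved for a lesion when all repeat ablations of that lesion (target and non-target lesions) are defined as complete ablation". For the patient-level summary, "secondary efficacy is achieved for a patient when all re-ablations of target lesions and all re-ablations of non-target lesions are defined as a complete ablation".

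**Denominator.** For lesions, SAP 8.6 takes "lesions that had a repeat ablation during visit 3 to visit 14 including unscheduled visits". It does not mention progression.

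**Data.** The protocol foresees more than one re-ablation. For NeuWave ablations during follow-up, the Schedule of Assessments footnote on technical success tells sites to "assess Technical success following each ablation". Protocol 12.3 adds: "Record follow-up post-ablation treatment, including the number of successful repeat ablations, if applicable".

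**Reporting.** Rates get two-sided 95% Clopper-Pearson intervals (SAP 8.6). SAP 8.7 plans no sensitivity analysis, so no alternative scoring will be shown.

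**The concern.** The definition asks whether a lesion has been successfully re-ablated. The scoring rule asks whether it was never incompletely re-ablated. The two part company for any lesion that needed more than one repeat session, which is where a measure of successful retreatment is most informative. One incomplete session fixes the lesion as a failure whatever follows.

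The denominator is a second, separate mismatch. Technique efficacy is assessed at Visit 3, while SAP 8.4.1 evaluates target lesion recurrence only from Visit 4. A target lesion re-ablated in the Visit 3 window because technique efficacy failed can enter the 8.6 denominator without any progression having been recorded. It would then be counted in a rate that the definition confines to lesions that progressed.

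At stake is a published rate whose label does not match its content, with no planned analysis that would reveal the difference.

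**Working it through.** The plan states no expected secondary efficacy rate, no sample size for it and no number of lesions with several re-ablations. There is no figure to reproduce, so the check has three parts.

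**1. Apply both rules to short histories** (C = complete, I = incomplete, in time order, all after local progression):

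| History | SAP 8.6 (all complete) | At least one complete | Last complete |
|---|---|---|---|
| C | success | success | success |
| CC | success | success | success |
| I | failure | failure | failure |
| II | failure | failure | failure |
| IC | failure | success | success |
| IIC | failure | success | success |
| ICC | failure | success | success |
| CI | failure | success | failure |

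Two things follow without any assumption. Success under 8.6 requires the first repeat ablation to be complete, so the lesion-level rate cannot exceed first-attempt completeness. And on the same lesions the 8.6 rate can never exceed the at-least-one rate.

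**2. Illustrate the size.** All inputs here are assumptions:
- q = probability that a repeat session is complete
- f = share of incompletely re-ablated lesions given one more session
- no session follows a complete one

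SAP 8.6 rate = q.
At-least-one rate = q + (1 − q) × f × q.

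- q = 0.85, f = 0.5: 0.85 + 0.15 × 0.5 × 0.85 = 0.914, against 0.85. Gap 6.4 points.
- q = 0.85, f = 1: 0.85 + 0.15 × 1 × 0.85 = 0.978, against 0.85. Gap 12.8 points.
- q = 0.80, f = 0.5: 0.80 + 0.20 × 0.5 × 0.80 = 0.88, against 0.80. Gap 8 points.
- q = 0.80, f = 1: 0.80 + 0.20 × 1 × 0.80 = 0.96, against 0.80. Gap 16 points.

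The second session may have its own completeness p2. The gap is then (1 − p) × f × p2, where p is first-attempt completeness. Over p from 0.70 to 0.95, f from 0.25 to 1 and p2 from 0.6 to 0.9, it runs from 0.05 × 0.25 × 0.6 = 0.75 points to 0.30 × 1 × 0.9 = 27 points. It is zero if no incompletely re-ablated lesion is later completed.

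To set the gap against sampling error, take 100 re-ablated lesions (also assumed) with q = 0.80 and f = 0.5. The 8.6 rule reports 80/100 (Clopper-Pearson 95% CI 70.8 to 87.3%). The at-least-one rule reports 88/100 (80.0 to 93.6%).

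**3. Denominator.** The definition requires local progression before the repeat ablation. SAP 8.6 requires only a repeat ablation between Visit 3 and Visit 14 or at an unscheduled visit. The documents do not say how many re-ablations would enter without recorded progression, or how those lesions would fare, so neither the size nor the direction of this effect can be given.

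**The case against.** The strongest reply is that the definition is silent on how to combine several sessions with mixed outcomes. It uses a plural, which could be read as all of them; the singular sentence that follows defines success of one ablation, not how sessions add up. Protocol 17.9 leaves full analysis details to the SAP. This stands in part: it is fair to say that 8.6 adds a condition the definition does not contain, and too strong to say that it breaks an explicit scoring rule. It does not remove the problem. On the plain reading, a lesion with history IC has had a successful repeat ablation, and 8.6 settles the ambiguity the other way without saying so.

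It can also be said that the rule is conservative and the endpoint secondary and descriptive. Both are true, and they limit the seriousness. But no hypothesis is tested (SAP 8.4), so there is no error rate for conservatism to protect, and a descriptive rate should match its label.

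On the denominator, 8.6 can be read as adding a visit window to a term that 8.4.2 already ties to progression. On that reading, restating the condition is a clarification. It is still needed, because 8.6 as written does not exclude the Visit 3 cases.

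Two stronger readings are tempting but unsupported:
- *Sites that retreat until complete look worse than sites that stop.* They do not: I and IC both score as failure. Retreatment after an incomplete session is uncredited, not penalised. A later session lowers a lesion's score only when every earlier one was complete. SAP 8.9 also plans no assessment of site homogeneity.
- *The patient-level rule contradicts the definition.* Protocol 17.5 lists secondary efficacy among patient-level outcomes, but the definition is a percentage of lesions and gives no patient-level rule to contradict. The patient-level rule shares the same feature and should follow whatever lesion rule is chosen.

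**Conclusion.** The point holds as a mismatch between definition and analysis, at lesion level. SAP 8.6 adds an all-sessions condition and omits the progression condition. The direction of the scoring effect is certain: on the same lesions, the planned rate is at or below the at-least-one rate.

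The size is not known. The range of about 6 to 16 points rests entirely on the assumed completeness of 80 to 85% per session and retreatment of 50 to 100% of incompletely re-ablated lesions. Other plausible inputs give less than 1 point or as much as 27, and the gap vanishes if rescue never occurs. The correction is worth making because it is cheap and no planned analysis would otherwise expose the difference. It does not affect the primary endpoints.

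**What to change.** Before database lock:

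1. In SAP 8.6, score a lesion as a success if it had at least one complete repeat ablation after recorded local progression. This is closest to 8.4.2. If the sponsor prefers last repeat ablation complete, that is also workable, but it is not the literal definition and must be stated in both 8.4.2 and 8.6. The two differ only for lesions with a complete session whose last session was incomplete, such as CI.
2. For the patient-level summary, require the chosen lesion rule to be met for every re-ablated lesion of that patient.
3. Restrict the denominator to lesions re-ablated after recorded local progression, and say how re-ablations after failed technique efficacy are handled.
4. Report first-attempt completeness, or the current all-sessions rule, as a separate line.

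The cost is SAP wording and one programming rule. The protocol already asks for technical success after each NeuWave re-ablation and for recurrence evaluation at every follow-up visit. Some lesions may still be unclassifiable. Per-ablation success is tied to NeuWave re-ablations, no explicit link from each re-ablation to a recorded progression is described, Protocol 17.9 expects missing data, and SAP 8.11 imputes none. The number of unclassifiable lesions should be reported.
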